5.3 Summary of Potential Risks and Benefits

As an optimized (bio-superior) second-generation antibody of the marketed product cetuximab, CetuGEX™ has the potential to become a considerably more active anti-EGFR antibody due to its significantly higher tumor-specific ADCC activity caused by the humanized and optimized glycosylation in the production process. At the same time the removal of non-human immunogenic Gal-Gal carbohydrate structures is expected to avoid the severe hypersensitivity reactions reported to be caused by non-human carbohydrate structures of cetuximab (in some geographical regions in about 22% of patients treated with cetuximab). Furthermore, CetuGEX™ opens the chance of therapeutic activity in otherwise unsuitable patients. As the key anti-tumor mode of action, ADCC is expected to be not only pronounced in patients with Fc γ RIIIa receptor allele status VV (8 - 27 % of the population) but also in those with FF and FV allotypes (73 - 92 % of the population), while the latter show no or very low anti-tumor ADCC activity with cetuximab. Therefore extended patient populations may benefit from the potential anti-tumor activity of CetuGEX™ in the clinic. The well-known cutaneous

toxicity occurring in up to 90% of patients treated with the approved anti-EGFR antibodies cetuximab and panitumumab (Vectibix®) is clearly linked to the EGFR inhibition in the skin and correlates with the anti-tumor efficacy of the antibody. This was also observed in the patients treated with CetuGEXTM, although from first evidence with lower incidence and grade. The phase 1 study showed reasonable tolerability with an expected high incidence of IRRs (mostly grades 1 and 2, few grade 3 and no grade 4) in conjunction with a considerable activity, given the far advanced cancer population.

Immediate allergic infusion reactions are unlikely; however IRRs of low grade were very common with this compound. As in general, although it didn't happen in the reported study, any infusion reaction has the potential to occur as life threatening severe reaction like a hypertensive crisis associated with neurologic signs and symptoms, wheezing, oxygen desaturation, chest pain, headaches, rigors, and diaphoresis, cardiac emergencies, anaphylaxis, cytokine release syndrome, convulsions, or hypotension, monitoring for these events will be cautiously undertaken.

In conclusion, the benefit-risk balance is deemed positive.

5.4 Rationale

Cancers of the head and neck, primarily tumors of the oral cavity, pharynx and larynx, account for > 5% of all malignancies. Most head and neck cancers, approximately 90% in Western societies, are SCCHN. Tobacco and alcohol use are the most important risk factors for the development of head and neck cancers. Beside cigarette smoke, chewing of tobacco increases the risk for cancers of the oral cavity. Smoking pipes may lead to cancer of the lip and tongue. The detrimental effect of tobacco is further enhanced by alcohol abuse and by poor oral hygiene. Further risk factors are virus infections caused by Epstein-Barr virus and human papilloma viruses. Due to the drinking and smoking habits, many patients also suffer from concomitant diseases such as coronary artery disease, chronic bronchitis or liver cirrhosis.

Treatment of head and neck cancer varies depending on localization, spread and histological subtype. The primary therapy option is surgery with excision of the primary tumor combined with extensive neck dissection. For advanced-stage disease, surgery and radiotherapy are often combined with chemotherapy usually delivered postoperatively. For unresectable disease, combined chemotherapy and radiotherapy has become the standard of care. The majority of patients presenting in a more advanced disease stage will eventually relapse either loco regional and/or at distant sites^{9,10}. Patients with recurrent and/or metastatic disease who are not candidates for local therapies are usually offered chemotherapy, with the goal of prolonging survival and controlling symptoms. Platinum based chemotherapy is the current standard of care in patients with recurrent and/or metastatic SCCHN and since 2008 a new targeted therapy, cetuximab, showed benefit by prolonging overall survival in addition to platinum-based chemotherapy and 5-FU without modifying the characteristic AE profile of platinum-based chemotherapy and without negative impact on quality of life (QoL). Platinum based chemotherapy plus cetuximab is the current standard of care in patients with recurrent and/or metastatic SCCHN⁹. Recurrent and metastatic SCCHN still carries a poor prognosis. The median

survival of patients with recurrent and/or metastatic SSCHN is 6-9 months and the 1-year survival is 20-40%⁹.

The clinical conduct of this study is planned in accordance to the guidance document of the International Conference of Harmonization (ICH) on Good Clinical Practice (GCP) and study design is chosen in accordance with the published guidelines on the clinical investigation of human normal immunoglobulin for intravenous administration (IVIgs) (EMA/CHMP/BPWP/94033/2007), on similar biological medicinal products containing monoclonal antibodies – non-clinical and clinical issues (EMA/CHMP/BMWP/403543/2010) and on the evaluation of anticancer medicinal products in man (CHMP/EWP/205/95).

6 OBJECTIVES

6.1 Primary Objective

The primary objective of the study is to evaluate the efficacy of CetuGEX™ for the treatment of patients with stage III/IV recurrent and/or metastatic SCCHN as compared to cetuximab (both in combination with platinum-based chemotherapy) in terms of PFS.

6.2 Secondary Objectives

Secondary objectives are as follows:

1. To evaluate further efficacy criteria, safety and QoL of patients with stage III/IV recurrent and/or metastatic SCCHN treated with CetuGEX™ as compared to cetuximab (both in combination with platinum-based chemotherapy).
2. To assess PK parameters and profiles of CetuGEX™.
3. To assess efficacy and safety based on genetic markers for immune response (FcγR allotypes) and biomarkers.

7 STUDY DESIGN

7.1 Overall Study Design and Plan

7.1.1 Overview

This is a phase II, randomized, controlled, multicenter study with first line treatment (6 cycles of 5-FU and cisplatin in combination with CetuGEX™ vs. combination with cetuximab) followed by single-agent maintenance therapy (CetuGEX™ or cetuximab, respectively).

The randomization to CetuGEX™ vs. cetuximab will be performed using a 1:1 ratio and will be stratified by:

- FcγRIIIa status (FF or FV or VV)
- Oral cavity and oropharynx vs. other locations

- Locally recurrent vs. metastatic disease
- EGFR treatment naïve vs. EGFR treatment as part of multimodal therapy.

The study will include 3 separate study periods following screening:

Combination treatment phase:

Eligible patients will be randomized to receive as first line treatment either CetuGEX™ or cetuximab in combination with chemotherapy (5-FU and cisplatin) for the maximum duration of 6 cycles of combined treatment. In case of toxicity, chemotherapy can be dose reduced, discontinued or, if later than the first cycle, switched to carboplatin. If discontinued earlier for any other reason apart from progression, patients will start the maintenance phase at that time.

As soon as at least 10 patients per treatment arm have completed the second cycle of combination therapy, patient safety data will be reviewed by an independent data safety monitoring board (DSMB).

Single-agent maintenance phase:

After completion or discontinuation of combination chemotherapy for any other reason apart from progression, the treatment will be followed by maintenance therapy with CetuGEX™ alone or cetuximab alone, respectively. Single-agent maintenance therapy will be continued until progression of disease or limiting toxicity.

Follow-up:

A Safety Visit must be performed 28 (+2) days after the last administration of the study drug for all randomized patients. In case of treatment discontinuation due to reasons other than disease progression, patients will stay on the regular study schedule until disease progression is documented and will then attend a Final Examination Visit. In case of treatment discontinuation due to disease progression, the Safety Visit is identical to the Final Examination Visit.

After the Final Examination, patients will be followed-up by quarterly phone calls until death or for a maximum duration of 24 months after randomization of the last patient for assessment of overall survival.

An overview on the duration of each study period as well as the overall study duration is provided in Section 10.2.

7.1.2 Endpoints

The primary efficacy endpoint is the progression-free survival (PFS) as assessed by the investigator.

Secondary endpoints are:

Efficacy endpoints:

- PFS as assessed by independent centralized reading
- Objective response rate (ORR; i.e., complete response [CR] + partial response [PR]) at the end of combination treatment
- Best overall response rates (including maintenance therapy treatment)
- Clinical benefit rate (CBR; i.e., CR + PR + stable disease [SD])
- Duration of response
- Overall survival (OS)
- Time to treatment failure (TTF)
- QoL scores as assessed by European Oncology Research Trials Committee (EORTC) QoL questionnaires (QLQ) EORTC-QLQ-C30 and EORTC-QLQ-H&N35.

In addition, PFS and all secondary efficacy endpoints listed above will be analyzed by FcγRIIIa-allotype subgroups (i.e., FF, FV and VV), by p16 status, by EGFR status, and other potential parameters, unless the sample sizes in subgroups are too low.

Pharmacokinetic endpoints:

Antibody trough levels and PK profiles of CetuGEX™ will be assessed throughout the study.

Safety endpoints are:

- Incidence of AEs and serious AEs, including incidence of target/class-specific side effects (skin reactions, diarrhea)
- IRRs
- Physical and laboratory assessments
- Vital signs
- Electrocardiogram (ECG)

In addition, the incidence of AEs will be analyzed by FcγRIIIa-allotype subgroups (FF, FV, VV).

Exploratory endpoints are:

- Immunogenicity: incidence of anti-drug antibodies (ADAs)
- Immunological parameters: cytokine levels and immune cell status.

7.3 Study Site(s)

The study will take place at approximately 40 sites in Europe and the USA. Each site is anticipated to screen a sufficient number of patients to be able to randomize a total of approximately 240 patients.

7.4 Point of Contact

A point of contact will be identified to provide information to patients about where to obtain information on the study, the rights of the patient, and whom to contact in case of study-related injury. This information will be provided in the patient information and informed consent form (ICF).

8 PATIENT POPULATION

8.1 Selection of Study Population and Diagnosis

It is planned to randomize approximately 240 adult patients with stage III/IV recurrent and/or metastatic SCCHN. An enrollment log of enrolled patients must be maintained at each study site.

8.2 Study Entry Criteria

8.2.1 Inclusion Criteria

A patient will be eligible for study participation if the patient meets all of the following criteria:

1. Patients with histologically confirmed recurrent and/or metastatic SCCHN not eligible for local treatment.
2. Patients with measurable disease according to Response Evaluation Criteria in Solid Tumors (RECIST) 1.1.
3. Patients aged at least 18 years at screening.
4. Eastern Cooperative Oncology Group (ECOG) performance status of 0 or 1.
5. Minimum life expectancy of 3 months.
6. Tissue samples available for specific disease and therapy related biological assessments.
7. If female and of childbearing potential, is non-lactating and has negative pregnancy test results at screening and prior to randomization.
8. If female, is either not of childbearing potential (defined as postmenopausal for at least 1 year or surgically sterile [bilateral tubal ligation, bilateral oophorectomy, or hysterectomy]) or willing to use highly effective contraceptives during study participation until 6 months after last administration of any study medication, particularly cisplatin or carboplatin, with a failure rate < 1% according to the Note for Guidance on non-clinical safety studies for the conduct of human clinical trials and marketing authorization for pharmaceuticals (CPMP/ICH/286/95) of the European Medicines Agency (EMA).
Male patients who have partners of childbearing potential have to confirm adequate use of highly effective contraceptives during study participation until 6 months after last administration of any study medication, particularly cisplatin or carboplatin, as well.
9. Willing and able to comply with the protocol.
10. Willing and able to provide written informed consent.

8.2.2 Exclusion Criteria

A patient will be excluded from the study if the patient meets any of the following criteria:

1. Prior systemic chemotherapy, except if given as part of a multimodal treatment for locally advanced disease which was completed more than 6 months prior to randomization.
2. Cetuximab or other EGFR targeting agent treatment, except if given as part of a multimodal treatment for locally advanced disease which was completed more than 6 months prior to randomization.
3. Surgery (other than minor interventions like diagnostic biopsy or intravenous port implantation) or irradiation within 30 days before randomization.
4. Concomitant anti-tumor therapy or concomitant immunotherapy, live vaccines including yellow fever vaccination (as per cisplatinum Summary of Product Characteristics [SmPC, Appendix F]).
5. Concomitant corticosteroid treatment unless specified within the protocol.
6. Clinical evidence of brain metastasis or leptomeningeal involvement.
7. Patients with nasopharyngeal tumors.
8. Concomitant malignant disease, except for adequately treated tumors with high likelihood of being cured (e.g., basal cell cancer of the skin, cervical cancer or breast cancer in situ). Patients with previous malignancies but without evidence of disease for at least 5 years will be allowed to enter the study.
9. Patients with renal or hepatic impairment (serum creatinine and bilirubin > 1.5 fold above the upper limit of normal ranges, creatinine clearance < 60 ml/min, and transaminase > 5 fold above the upper limit of normal ranges) and patients with hematology parameters outside the normal ranges (hemoglobin < 9 g/dl, absolute neutrophil count < 1500/mm³ and platelet count < 10⁵/mm³) at screening as well as patients with impaired auditory function or platinum-related neuropathy.
10. Clinically active infections \geq Grade 2 using National Cancer Institute (NCI) Common Terminology Criteria for Adverse Events (CTCAE) version 4 and/or requiring intravenous antibiotics.
11. Known active hepatitis B or C.
12. Known human immunodeficiency virus (HIV) infection.
13. Myocardial infarction within 6 months prior to screening.
14. Symptomatic congestive heart failure (New York Heart Association [NYHA] Grade 3 or 4), unstable angina pectoris within 6 months prior to screening, significant cardiac arrhythmia, history of stroke or transient ischemic attack within 1 year prior to screening.
15. History of keratitis requiring medical interventions within the last 5 years or interstitial lung disease.

16. Patients with any other disorder that, in the opinion of the investigator, might interfere with the conduct of the study.
17. Patients with an unstable condition (e.g., psychiatric disorder, a recent history of drug or alcohol abuse, interfering with study compliance, within 6 months prior to screening) or otherwise thought to be unreliable or incapable of complying with the requirements of the protocol.
18. Patients institutionalized by official means or court order.
19. Receipt of any other investigational medicinal product within the last 30 days before randomization or any previous CetuGEX™ administration.
20. Prior allergic reaction to a monoclonal antibody, grade 3 IRR or any grade 4 reaction to a monoclonal antibody.
21. Known sensitivity to any component of the investigational medicinal product (IMP) and medication used in this study.

8.3 Premature Patient Withdrawal

All patients will be advised that they are free to withdraw from participation in this study at any time, for any reason, and without prejudice. Every reasonable attempt should be made by the investigator to keep patients in the study; however, patients must be withdrawn from the study if they withdraw consent to participate. Investigators must attempt to contact patients who fail to attend scheduled visits by telephone or other means to exclude the possibility of an AE being the cause of withdrawal. Should this be the cause, the AE must be documented, reported, and followed as described in Section 11.2.

The sponsor reserves the right to request the withdrawal of a patient due to protocol violations or other reasons.

The investigator also has to withdraw patients from the study at any time for the following reasons:

- Unacceptable toxicity
- More than 3 weeks delay of scheduled infusion of CetuGEX™/cetuximab (i.e., missing more than 2 consecutive infusions)
- Intercurrent illness interfering with study procedures
- Noncompliance with study procedures, or
- Pregnancy.

If a patient is withdrawn from treatment prior to PD due to unacceptable toxicity or any other reasons as detailed above except noncompliance with study procedures, the patient will remain on regular study schedule until progression of disease unless this might interfere with the patient's best interest.

If a patient is withdrawn from the complete study before documented progressive disease, the reason for withdrawal and the date of discontinuation will be recorded on the appropriate electronic case report form (eCRF). Whenever possible, the evaluations that were to be conducted at the Final Examination should be performed at the time of premature discontinuation.

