9.13 Treatment After End of Study

After the end of the study, i.e., in case of progression of disease or if other withdrawal criteria are met, patients will be treated by their physician according to most appropriate and best supportive standard of care.

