13.2 Sample Size Determination

The log-rank test will be used to test the hypothesis that patients assigned to the CetuGEX™ arm have increased PFS compared to patients assigned to the control arm. The sample size calculation is based on the following assumptions:

- The median PFS in the control arm is expected to be 5.6 months¹⁵ post randomization.
- It is expected that the median PFS in the CetuGEX™ arm can be increased to 8.4 months corresponding to a hazard ratio of 0.67.
- The overall trial duration will be approximately 48 months with an anticipated recruitment time of 24 months, anticipated treatment phase until PFS events are reached of approximately 12 months after randomization of the last patient (data cut-off for main analysis) and ongoing follow-up for overall survival for at least 24 months after randomization of the last patient.
- Drop-outs are expected to occur at times following an exponential distribution and resulting in a drop-out rate of 10% at the cut-off for PFS analysis.
- Patients will be randomized in a 1:1 ratio.
- The overall two-sided significance level will be 0.05 and the power to be maintained 80%.

Based on these assumptions, approximately 240 patients have to be randomized to observe the required overall number of 192 events.

Assuming a corresponding effect on OS (hazard ratio 0.67) and a median overall survival of 10.6 months in the control group the number of survival events to be observed after a 24 months follow-up for survival will be 183.

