### **5. SAMPLE SIZE DETERMINATION**

Approximately 240 patients will be randomized in this study.

The log-rank test will be used to test the hypothesis that patients assigned to the CetuGEX™ arm have increased PFS compared to patients assigned to the control arm.

The sample size calculation is based on the following assumptions:

- The median PFS in the control arm is expected to be 5.6 months post randomization.
- It is expected that the median PFS in the CetuGEX™ arm can be increased to 8.4 months corresponding to a hazard ratio of 0.67.
- The overall trial duration will be approximately 36 months with an anticipated recruitment time of 24 months, anticipated treatment phase until PFS events are reached of approximately 12 months after randomization of the last patient (data

cut-off for main analysis) and ongoing follow-up for overall survival for at least 24 months after randomization of the last patient.

- Drop-outs are expected to occur at times following an exponential distribution and resulting in a drop-out rate of 10% at the cut-off for PFS analysis.
- Patients will be randomized in a 1:1 ratio.
- The overall two-sided significance level will be 0.05 and the power to be maintained 80%.

Based on these assumptions, approximately 240 patients have to be randomized to observe the required overall number of 192 events.

If the required number of events is not reached as planned after 12 months from last patient randomized, the main analysis will be postponed to obtain more events but not more than additional 6 months.

Assuming a corresponding effect on OS (hazard ratio 0.67) and a median overall survival of 10.6 months in the control group the number of survival events to be observed after a 24-months follow-up for survival will be 183.

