Variable Name	Computation Methods, Notes, or Equation(s)		
PFSp  (primary definition)	= Earliest date of progression or death - date of randomization + 1 The earliest date of PD will be used irrespective of PD confirmation		
	Finding	Date of PD of Censoring	Outcome
	No PD or death	Pre and post-baseline imaging done: Date of last imaging	Censored
		No baseline or no post-baseline imaging done: Date of randomization	Censored
	Progression/death documented after a new anticancer treatment has started PD at scheduled visit PD between scheduled visits	Date of last imaging prior to new anticancer treatment Date of imaging Date of imaging	Censored Event Event
PFSs  (sensitivity definition)	= Earliest date of progression or death - date of randomization + 1 The earliest date of PD will be used irrespective of PD confirmation		
	Finding	Date of PD of Censoring	Outcome
	No PD or death	Pre and post-baseline imaging done: Date of last imaging	Censored
		No baseline or no post-baseline imaging done: Date of randomization	Censored
	Progression/death documented after a new anticancer treatment has started PD at scheduled visit PD between scheduled visits*	Date of last imaging prior to new anticancer treatment. Date of imaging Date of next scheduled visit	Censored Event Event
	PD after 2 or more missing scheduled visits	Date of last imaging prior to first missing visit.	Censored
	Death up to 16 weeks (112 days) after last imaging Death later than 16 weeks (112 days) after last imaging	Date of death Date of last imaging	Event Censored
Best overall response	Best modified irRC classification (CR, PR or SD) as assessed by the investigator or by the independent centralized review		

(rates) (BO(R))	SD: follow-up measurements must have met the SD criteria at least once after randomization at a minimum interval of 8 weeks.
Objective response (rate) (OR(R))	Best response of CR or PR
Clinical benefit (rate) (CB(R))	Best response of CR or PR or SD. SD: follow-up measurements must have met the SD criteria at least once after randomization at a minimum interval of 8 weeks

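### Protocol 8.3 exempts patients withdrawn for noncompliance from continued scans, contrary to 7.1.1 and SAP 3.1, so primary PFS may be informatively censored

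*Protocol*

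**What the plan says.** Protocol 8.3 lists reasons for which the investigator must withdraw a patient: unacceptable toxicity, more than 2 consecutive missed infusions, intercurrent illness, noncompliance with study procedures, and pregnancy. It then sets the follow-up rule for patients withdrawn from treatment before progression. After naming toxicity, the sentence reads: "any other reasons as detailed above except noncompliance with study procedures, the patient will remain on regular study schedule until progression of disease". A closing clause also releases patients where continuing would be against their best interest.

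Protocol 7.1.1 gives a different rule for patients who stop treatment for any reason other than progression: "patients will stay on the regular study schedule until disease progression is documented and will then attend a Final Examination Visit". The Synopsis and SAP 3.1 say the same. None of the three names an exception for noncompliance.

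The primary endpoint is investigator-assessed PFS (Protocol 7.1.2) in an open-label trial (9.6). In the primary definition (PFSp, SAP 7.2), a patient with no progression or death is censored by the rule "Pre and post-baseline imaging done: Date of last imaging". Survival calls continue after the Final Examination (Protocol 10.1.5), and PFSp takes the earlier of progression and death. On drop-out, Protocol 13.2 assumes: "Drop-outs are expected to occur at times following an exponential distribution".

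**The concern.** Sites have two incompatible instructions for collecting the primary endpoint. If they follow 8.3, imaging stops for a reason that arises after randomization and that an investigator who knows the arm has to label. Neither document defines noncompliance. A patient who stops attending could be recorded as having missed more than 2 infusions, which keeps the scans, or as noncompliant, which ends them.

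If the label is used more readily for patients who are deteriorating, or more readily in one arm, the censoring is related to outcome. The log-rank comparison would then be biased. Scans that were never taken cannot be recovered at analysis.

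**Working it through.** **1. The rules side by side.**

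| Reason for stopping | Protocol 8.3 | Synopsis, Protocol 7.1.1, SAP 3.1 |
|---|---|---|
| Toxicity, intercurrent illness, more than 2 missed infusions, pregnancy | Scans continue (best-interest clause applies) | Scans continue |
| Noncompliance | Not required to continue | Scans continue |

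The rules differ only for noncompliance.

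**2. A noncompliant patient followed through the PFS definitions (SAP 7.2).**

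- Alive, no progression recorded: censored at the last scan, or at randomization if there was no post-baseline scan.
- Dies, no new anticancer treatment first: an event at the death date under PFSp. Under the sensitivity definition PFSs it is an event only if death falls within 112 days of the last imaging; otherwise the patient is censored at that imaging.
- New anticancer treatment first: censored at the last imaging before it. Protocol 10.1.5 records only post-progression therapies after the Final Examination, so it is unclear whether this information would exist for a patient withdrawn before progression.

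Under PFSp, the time after the last scan therefore counts if the patient dies and not if the patient survives. Missed progressions understate that arm's hazard, while counting only the deaths overstates it. The documents do not fix the net direction. The Final Examination includes no imaging (Protocol 10.1.5), so there is no exit scan either.

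**3. The plan's own figures.** Inputs from Protocol 13.2 and SAP 5: "The overall two-sided significance level will be 0.05 and the power to be maintained 80" percent; "The median PFS in the control arm is expected to be 5.6 months"; the CetuGEX median "can be increased to 8.4 months corresponding to a hazard ratio of 0.67"; 1:1 allocation; 24 months' accrual plus 12 months' follow-up; 10% drop-out.

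- Events (Schoenfeld): 4(z₀.₉₇₅ + z₀.₈₀)² / (ln HR)², with HR = 5.6/8.4 = 0.667. This gives 4 × 7.849 / 0.1644 = 191, against 192 stated.
- Event probability: 1 − [exp(−12λ) − exp(−36λ)]/(24λ), with λ = ln 2/median. This gives 0.928 for control and 0.838 for CetuGEX, so 111.3 + 100.6 = 211.9 events in 240 patients without drop-out.
- With 10% drop-out: 211.9 × 0.9 = 190.7 events, so N = 240 × 192/190.7 = 241.6. Treating drop-out as a competing exponential risk observed in 10% of patients gives 194.0 events and N = 237.6. The plan states 240.

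The design reproduces, and the exception changes none of these figures. The issue is bias.

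**4. Size, under assumed rates.** The documents give no noncompliance rate. A rough figure: of 192 events, about 96 fall in each arm, and 5% of 96 is 4.8. Losing these scales that arm's hazard by about 0.95, giving 0.667 × 0.95 = 0.63 (CetuGEX loss) or 0.667/0.95 = 0.70 (control loss).

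A simulation of 4,000 trials per row (120 per arm, exponential PFS, the accrual and drop-out above) censors each affected patient at the last 6-weekly scan before progression and never counts a later death:

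| Loss | True HR 1: mean HR | Two-sided error | Error favouring CetuGEX | True HR 0.667: mean HR | Rejection rate |
|---|---|---|---|---|---|
| None | 1.00 | 4.8% | 2.3% | 0.66 | 80.9% |
| 5%, both arms | 1.00 | 5.2% | 2.7% | 0.66 | 79.4% |
| 5%, CetuGEX only | 0.955 | 6.6% | 5.4% | 0.63 | 87.8% |
| 5%, control only | 1.05 | 6.4% | 1.0% | 0.69 | 68.2% |
| 10%, CetuGEX only | 0.91 | 9.8% | 9.4% | 0.60 | 92.8% |
| 10%, control only | 1.10 | 10.3% | 0.5% | 0.73 | 55.7% |

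Monte Carlo standard error near 5% is √(0.05 × 0.95/4000) = 0.34 percentage points. The estimator gives 0.660 with no loss, so the shifts due to the loss alone are 0.630/0.660 = 0.955 and 0.694/0.660 = 1.05.

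**5. What the planned analyses do.** PFSs censors more: it also drops progression after two or more missed visits. Central reading depends on the same scans. The per-protocol, Cox and site-adherence analyses (SAP 9.1) do not address informative censoring.

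**The case against.** The strongest reply is that the patients most likely to bias PFS are already protected. Toxicity, intercurrent illness and more than 2 missed infusions are separate reasons in 8.3, and all keep the scans. Investigators must also contact patients who miss visits, to exclude an adverse event as the cause. What is left may be a small group that would not attend scans anyway. This stands as a limit on size. It does not remove the overlap between labels or the conflict between sections.

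Some stronger readings are tempting, but the documents do not support them:

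- That noncompliance is the only way out of imaging. The best-interest clause and withdrawal of consent also release patients. Noncompliance is the only listed reason exempted outright, and 8.3 lifts an obligation without forbidding scans.
- That Protocol 9.13 ends follow-up for these patients. It reads "in case of progression of disease or if other withdrawal criteria are met, patients will be treated by their physician", and so treats progression in the same way, although survival calls continue after progression. It concerns care after study treatment.
- That noncompliance reflects decline or dislike of the allocated arm. This is a reasonable inference in an open-label trial, but the documents give no mix of reasons.
- That the exponential drop-out assumption is a flaw in the analysis. It is a sample-size input only.

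PFSs partly answers the uneven counting of deaths, by censoring those more than 112 days after the last imaging. TTF counts every discontinuation, but as a secondary endpoint. Withdrawals are tabulated by reason and arm (Protocol 13.4.2.1), so an imbalance would be visible but not corrected.

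**Conclusion.** The contradiction is established, and the risk of informative censoring in the primary PFS follows if 8.3 is applied as written. The size of that risk is not established. The figures of about 0.63 or 0.69 for a true hazard ratio of 0.667, and about 6.5% two-sided error under the null, need three assumptions: 5% of one arm affected and none of the other, every affected patient just short of progression, and no later death counted. PFSp would in fact count some of those deaths. These are upper-end illustrations at that rate, and a reader should not take them as an expected bias. With 5% lost in both arms the hazard ratio is essentially unchanged. The point is worth correcting because the remedy is cheap and the missing scans could not be replaced later. The 192-event, 240-patient design is unaffected.

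**What to change.** Reconcile Protocol 8.3 with 7.1.1 and SAP 3.1 by deleting the noncompliance exception from the follow-up sentence. Tumor assessments and survival status are then sought for these patients until progression or death, subject to consent, with routine-care scans collected if study visits are refused. Keep the best-interest clause. Leave the treatment-withdrawal reasons and the pregnancy rule (Protocol 11.3.2) as they are; this change concerns data collection only.

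In SAP 9.1, add a PFS sensitivity analysis that counts study withdrawal before progression as an event: in both arms, then in each arm in turn.

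The cost is one sentence in an amendment, a note to sites, a few scans that 7.1.1 already foresees, and one added set of analyses. Some of these patients will still not attend, so the gap would narrow but not close; the sensitivity analysis covers what remains.
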